12.7.5.4 Drug of Abuse Screen

Drug of abuse screen is planned to be collected at Screening and Period 1 Day 1 H0.

A by-patient listing presenting all THC measures along with urinary drug screen results will also be provided.

12.7.5.5 Pregnancies

Any reported positive pregnancy results or reported pregnancies will be listed.

12.7.5.6 Examination of Oral Mucosa

Based on the Safety Analysis Set, results of oral mucosa examination (normal, abnormal NCS and Abnormal CS) planned to be performed at Screening, Day 1 H0, Day 15 and Day 21 of each period and during the follow-up visit will be described by treatment arm according to baseline status.

Each patient presenting at least one abnormal assessment will be listed.

12.7.5.7 Covid-19 Impact

The impact of COVID-19 on each visit will be summarized by treatment arm and a by-patient listing presenting patients impacted by COVID-19 during the conduct of the trial will be provided.

14.0 Glossary of Abbreviations

Glossary of Abbreviations:	
11-COOH-THC	11-carboxy- Δ^9 -tetrahydrocannabinol
11-OH-THC	11-hydroxy- Δ^9 -tetrahydrocannabinol
7-COOH-CBD	7-carboxy-cannabidiol
7-OH-CBD	7-hydroxy-cannabidiol
ADaM	Analysis dataset model
ADL	Activity of Daily Living
AE	Adverse event
AESI	Adverse events of special interest
ANTE(1)	first order ante-dependence
ATC	Anatomic Therapeutic Class
ET visit	End of Treatment visit
ALT	Alanine aminotransferase
ALP	Alkaline phosphatase
AST	Aspartate aminotransferase
BLQ	Below Limit of Quantification
BDZ	Benzodiazepine
BMI	Body Mass Index
bpm	Beats per minutes
CBD	Cannabidiol
CDF	Cumulative distribution function
CFB	Change from baseline
CI	Confidence interval
CRF	Case report form
CS	Compound symmetry
CS	Clinically significant
CSR	Clinical study report
C-SSRS	Columbia-Suicide Severity Rating Scale
CTCAE	Common Terminology criteria for adverse events
CTMS	Clinical Trial Management System
CV	Coefficient of variation
D	Day
DBP	Diastolic blood pressure

DILI	Drug-Induced Liver Injury
DISH	drug-induced serious hepatotoxicity
DMD	Disease Modifying Drug
DRESS	Drug reaction with eosinophilia and systemic systems
ECG	Electrocardiogram
eCRF	Electronic case report form
EDC	Electronic data capture
eDiary	Electronic diary
eGFR	Estimated Glomerular filtration rate
FAS	Full Analysis Set
FU	Follow-up
GEE	Generalized estimating equation
GGT	Gamma-glutamyl transferase
GW	GW Pharma Ltd / GW Pharma Limited
H	Hour
HLGT	High Level Group Term
HLT	High Level Term
HR	Heart rate
hrs	hours
ICF	Informed consent form
ICH	International Council for Harmonisation
IES	Intercurrent event(s) strategy
IMP	Investigational medicinal product
INR	International normalized ratio
IPD	Important protocol deviation
IRT	Interactive response technology
kcal	Kilo calories
KM	Kaplan-Meier
KR	Kenward-Roger
KR2	Kenward-Roger method (e.g., KR2, 2009 version)
LLMT	Lower Limb Muscle Tone
LLMT-4	Lower Limb Muscle Tone-4
LLMT-6	Lower Limb Muscle Tone-6
LLMT-10	Lower Limb Muscle Tone-10
LLN	Lower Limit of Normal

LME	Linear mixed-effects
LS mean	Least square mean
LSMD	Least square mean difference
M	Month
MAR	Missing at Random
MAS	Modified Ashworth Scale
Max	Maximum
MCMC	Markov Chain Monte Carlo
MDRD	Modification of Diet Renal Disease
MedDRA	Medical Dictionary for Regulatory Activities
MHP	Mobile Health Platform
MI	Multiple Imputation
Min	Minimum
MNAR	Missing Not At Random
MS	Multiple sclerosis
msec	millisecond
MSSS-88	Multiple Sclerosis Spasticity Scale
NC	Not Calculated
NCS	Not Clinically significant
NRS	Numerical Rating Scale
OR	Odds ratio
P	Period
PD	Pharmacodynamic
PK	Pharmacokinetic
PLS	Population-level summary
PP	Per Protocol
PRA	Pharmaceutical Research Associates
PRN	pro re nata (meaning as-needed)
PRO	Patient reported outcome
PSO	Predictive Study Operations
PT	Preferred term
Q1	First Quartile / Quartile 1
Q3	Third Quartile / Quartile 3
QTc B	QT corrected Bazett's formula
QTc F	QT corrected Fridericia's formula

SAE	Serious adverse event
SAP	Statistical analysis plan
SBP	Systolic Blood Pressure
SD	Standard deviation
SDTM	Study data tabulation model
SE	Standard error
SI	Standard International
SOC	System organ class
T25FW	Timed 25-Foot Walk
TBL	Total bilirubin
TEAE	Treatment-emergent adverse event
THC	Δ^9 -Tetrahydrocannabinol
UK	United Kingdom
ULN	Upper limit of normal
UN	Unstructured
WHO-DD	World Health Organization-Drug Dictionary
Y	Year

Appendix 1 Classification of Protocol Deviations

List of Important Protocol Deviation Category

Number	IPD category
01	Inclusion criteria
02	Exclusion criteria
03	Study drug
04	Assessment safety
05	Efficacy/pharmacodynamic endpoint
06	Visit window
07	Prohibited co-medication
08	Others

List of Major Important Protocol Deviations

Number	Major IPD category	Major IPD criteria
01	Inclusion criteria	Does not have a MAS untransformed score of at least 2 in 2 or more of six muscle groups (right knee flexors, left knee flexors, right knee extensors, left knee extensors, right plantar flexors, or left plantar flexors) at Visit 1.
02	Exclusion criteria	Has taken nabiximols, cannabis, or a cannabis-derived product for medicinal or recreational purposes in the 30 days prior to Visit 1 and unable to abstain for the duration of the trial.
03	Exclusion criteria	Did not respond adequately to treatment with nabiximols or another cannabis-based medication if exposed at any time before the 30-day period prior to Visit 1.
04	Exclusion criteria	Any concomitant disease or disorder that has spasticity-like symptoms or that may influence the patient's level of spasticity.
05	Exclusion criteria	Has had a relapse of MS within the 60 days prior to Visit 1.
06	Exclusion criteria	Clinically suspected to have a contracture in one of the muscle groups of the lower limbs, preventing assessment with the MAS.
07	Exclusion criteria*	Has any other clinically significant disease or disorder (including seizure disorder) that, in the opinion of the investigator, may put the patient at risk because of participation in the trial, influence the interpretation of trial results, or may affect the patient's ability to take part in the trial. For certain disorders, determined with medical monitor
08	Study drug	Subject taking more than 13 sprays per day at any time during each treatment phase.
09	Study drug	Patient randomized but not exposed to study drug.
10	Study drug	Subject not receiving at least 1 spray in the morning on the last day during maintenance phase.
11	Study drug	Subject receiving IMP during the washout period.
12	Study drug	Subject not exposed to IMP during at least 1 day during titration or the maintenance phase.
13	Study drug	Patient receiving a kit number not allocated by IXRS which is not the treatment he/she was allocated to by IXRS during this period.
14	Efficacy endpoint	Missing evaluable MAS LLMT-6 pre-dose assessment.
15	Efficacy endpoint	Missing evaluable MAS LLMT-4 pre-dose assessment.
16	Efficacy endpoint	Missing evaluable MAS LLMT-6 at endpoint. (Day 21 or Day 51)
17	Efficacy endpoint	Missing evaluable MAS LLMT-4 at endpoint. (Day 21 or Day 51)
18	Visit window	Wash-out duration of less than 7 days.
19	Visit window	During maintenance phase: Visit 4 occurred +/- 2 days out of window Visit 5 occurred +/- 3 days out of window Visit 6 occurred +/- 2 days out of window Visit 8 occurred +/- 2 days out of window Visit 9 occurred +/- 3 days out of window
20	Prohibited co-medication	Patient taking antipsychotic medication at any time during the trial.

Number	Major IPD category	Major IPD criteria
21	Prohibited co-medication	Patient taking benzodiazepine on an as needed (PRN) basis during the trial.
22	Prohibited co-medication	Patient taking commercial cannabis or any cannabinoid medication during the trial.
23	Prohibited co-medication	Patient taking botulinum injection during the trial.
24	Prohibited co-medication	Initiation or changes in the dose of MS disease modifying therapy any time after randomization at Visit 2
25	Prohibited co-medication	Initiation of a new course of physiotherapy any time after randomization at Visit 2

MS = *Multiple sclerosis*; MAS = *Modified Ashworth Scale*, IMP = *Investigational Medicinal Product*; IXRS = *Interactive x Response System*; LLMT-6 = *Lower Limb Muscle Tone-6*, LLMT-4 = *Lower Limb Muscle Tone-6*, PRN = *pro re nata meaning as needed*.

* Refers to *important protocol which may or not be considered as major important deviation*

Appendix 2 Clinical laboratory parameters

Biochemistry (Serum ¹)		Hematology (Whole Blood ¹)		Urinalysis (Urine ²)
Category	Parameters	Category	Parameters	Parameters
Hepatobiliary	Alanine aminotransferase	Red blood cells	Hematocrit	Blood
Hepatobiliary	Albumin	Red blood cells	Hemoglobin	Glucose
Hepatobiliary	Alkaline phosphatase	Red blood cells	Mean cell volume	Nitrites
Hepatobiliary	Aspartate aminotransferase	Red blood cells	Mean corpuscular hemoglobin	pH
Electrolytes and proteins	Calcium	Coagulation parameter	Platelets	Protein
Renal	Creatinine	Red blood cells	Red blood cell count	White blood cells
Hepatobiliary	Gamma-glutamyl transferase	White blood cells parameters	White blood cell count with automated differential	Specific gravity
Electrolytes and proteins	Potassium			Ketones
Electrolytes and proteins	Sodium			Urobilinogen
Hepatobiliary	Total bilirubin			Bilirubin
Electrolytes and proteins	Total protein			
Renal	Urea (blood urea nitrogen)			
Coagulation parameters	Prothrombin time (plasma ⁴)			

¹Analyzed at a central laboratory.

²Analyzed at the trial site by use of a dipstick (if allowed per local regulations).

³The standard drugs of abuse screen, including THC, will be analyzed by use of a urine dipstick at Visits 1 and 2. Patients will undergo a separate blood THC test at Visit 1 only.

⁴Analyzed at Screening (Visit 1) only.

Appendix 3 Unscheduled Clinical laboratory parameters

Biochemistry (Serum ¹)		Hematology (Whole Blood ¹)		Urinalysis (Urine ²)
Category	Parameters	Category	Parameters	Parameters
Hepatobiliary	Alanine aminotransferase	Red blood cells	Hematocrit	Blood
Hepatobiliary	Albumin	Red blood cells	Hemoglobin	Glucose
Hepatobiliary	Alkaline phosphatase	Red blood cells	Mean cell volume	Nitrites
Hepatobiliary	Aspartate aminotransferase	Red blood cells	Mean corpuscular hemoglobin	pH
Electrolytes, proteins and creatinine kinase	Calcium	Coagulation parameter	Platelet count	Protein
Renal	Creatinine	Red blood cells	Red blood cell count	White blood cells
Hepatobiliary	Gamma-glutamyl transferase	White blood cells parameters	White blood cell count	Specific gravity
Electrolytes, proteins and creatinine kinase	Potassium	White blood cells parameters	Total neutrophil count	Ketones
Electrolytes, proteins and creatinine kinase	Sodium	White blood cells parameters	Monocyte count	Urobilinogen
Hepatobiliary	Total bilirubin	White blood cells parameters	Lymphocyte count	Bilirubin
Electrolytes, proteins and creatinine kinase	Total protein	White blood cells parameters	Basophil count	Squamous epithelial cells
Renal	Urea (blood urea nitrogen)	White blood cells parameters	Eosinophil count	Mucus
Coagulation parameters	Prothrombin time (plasma4)			Microscopy
Hepatobiliary	Amylase			Leucocyte esterase
Electrolytes, proteins and creatinine kinase	chloride			Color
Electrolytes, proteins and creatinine kinase	Bicarbonate			Appearance
Lipids	HDL-Cholesterol			Bacteria
Lipids	LDL-Cholesterol			

Biochemistry (Serum¹)		Hematology (Whole Blood¹)		Urinalysis (Urine²)
Lipids	Total Cholesterol			
Lipids	Triglycerides			
Hepatobiliary	Lipase			
Electrolytes and proteins	Magnesium			
Electrolytes, proteins and creatinine kinase	Phosphorus			
Renal	Creatinine clearance			
Endocrinology	Insulin-like growth factor-1			
Endocrinology	Prolactin			
Renal	Estimate glomerular filtration rate			
Coagulation	INR			
Endocrinology	Glucose			
Electrolytes, proteins and creatinine kinase	Creatinine Kinase			
Immunology	HBsAg			
Immunology	HCV			
Immunology	HIV			

Appendix 4 Toxicity Criteria for Laboratory Hematology and coagulation Parameters based on CTCAE version 5.0

Laboratory Toxicity	Grade 1	Grade 2	Grade 3	Grade 4
Hematology				
Anemia (Hemoglobin Decreased)	<LLN – 6.2 mmol/L <LLN - 100 g/L <LLN – 10.0 g/L	<6.2 – 4.9 mmol/L <100 - 80 g/L <10.0 to 80.0 g/dL	<4.9 mmol/L <80 g/L <8.0 g/dL	
Hemoglobin increased	Increase in >0 - 2 g/dL	Increase in >2 - 4 g/dL	Increase in >4 g/dL	
White Blood Cells Decreased	<LLN – 3000/mm3 <LLN – 3.0 x 109/L	<3000 - 2000/mm3 <3.0 – 2.0 x 109/L	<2000 - 1000/mm3 <2.0 – 1.0 x 109/L	<1000/mm3 <1.0 x 109/L
Neutrophils count Decreased	<LLN – 1500/mm3 <LLN – 1.5 x 109/L	<1500 - 1000/mm3 <1.5 – 1.0 x 109/L	<1000 - 500/mm3 <1.0 – 0.5 x 109/L	<500/mm3 <0.5 x 109/L
Lymphocytes count Decreased	<LLN – 800/mm3 <LLN – 0.8 x 109/L	<800 – 500/mm3 <0.8 – 0.5 x 109/L	<500 - 200/mm3 <0.5 – 0.2 x 109/L	<200/mm3 < 0.2 x 109/L
Lymphocyte count increased		>4000/mm3-20,000/mm3 >4 - 20 x 109/L	>20,000/mm3 > 20 x 109/L	
Platelets count Decreased	<LLN – 75,000/mm3 <LLN – 75.0 x 109/L	<75,000 – 50,000/mm3 <75.0 – 50.0 x 109/L	<50,000 – 25,000/mm3 <50.0 – 25.0 x 109/L	<25,000/mm3 <25.0 x 109/L
Activated partial thromboplastin time prolonged (aPTT)	>ULN – 1.5 x ULN	>1.5 – 2.5 x ULN	>2.5 ULN °	

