12.7.3 Laboratory Data

The clinical safety laboratory data (hematology and biochemistry) are planned to be collected at Screening and Day 21 of each treatment period. In case of premature end of treatment the latest assessment collected on-treatment will be used as described in [Table 10.1-1](#).

For the purposes of summarization in both the tables and listings, all laboratory values will be converted to standardized units. The investigator and medical monitor will be provided with a list of the normal ranges used by the central clinical laboratory for all variables assayed during the trial and a statement of accreditation (or similar) for the laboratory. However, AST, ALT, GGT, ALP and total bilirubin will be summarized using SI units.

Only scheduled laboratory parameters defined in [Appendix 2](#) and those derived from them as eGFR (as defined in [Section 10.13](#)) will be included in summary tables and figures. However unscheduled laboratories values (coming from central or local laboratories) will be used in abnormality summary tables and will be presented in listings (using categories as defined in [Appendix 6 Abnormality Criteria](#)).

Baseline (Screening), Day 21 of each treatment period and the change from baseline to Day 21 (end of the treatment) will be summarized using the safety analysis set, by treatment arm, separately for red blood cells parameters and white blood cells parameters, hepatobiliary parameters, renal parameters, coagulation parameters and electrolytes and proteins (as described in [Appendix 2](#)). Furthermore, AST, ALT, GGT, ALP and total bilirubin will also be summarized as a multiple of the upper limit of normal (ULN).

Laboratory hematology and biochemistry (as described in [Appendix 2 Clinical laboratory parameters](#)) abnormalities will be evaluated, on patients from the Safety Analysis Set using shift tables at Day 21 according to baseline status with categories based on:

- reference ranges as either normal, below the lower limit of normal (LLN) as “Low” or above the ULN as “High”,
- based on CTCAE toxicity grade using version 5.0 or higher (as defined in [Appendix 4 Toxicity Criteria for Laboratory Hematology and coagulation Parameters](#) based on CTCAE version 5.0 for hematology parameters and in [Appendix 5 Toxicity Criteria for Laboratory Biochemistry Parameters](#) based on CTCAE version 5.0 for biochemistry parameters),

presented by treatment arm.

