Appendix 5 Toxicity Criteria for Laboratory Biochemistry Parameters based on CTCAE version 5.0

Laboratory Toxicity	Grade 1	Grade 2	Grade 3	Grade 4
Chemistry				
Sodium Increased (Hypernatremia)	>ULN - 150 mmol/L	>150 - 155 mmol/L	>155 - 160 mmol/L	>160 mmol/L
Sodium Decreased (Hyponatremia)	<LLN - 130 mmol/L		<130 - 120 mmol/L	<120 mmol/L
Potassium Increased (Hyperkaliemia)	>ULN - 5.5 mmol/L	>5.5 - 6.0 mmol/L	>6.0 - 7.0 mmol/L	>7.0 mmol/L;
Potassium Decreased (Hypokaliemia)	<LLN - 3.0 mmol/L	<LLN - 3.0 mmol/L	<3.0 - 2.5 mmol/L	<2.5 mmol/L
Calcium Increased (Hypercalcemia)	>ULN - 11.5 mg/dL; >ULN - 2.9 mmol/L Ionized calcium >ULN - 1.5 mmol/L	>11.5 - 12.5 mg/dL; >2.9 - 3.1 mmol/L Ionized calcium >1.5 - 1.6 mmol/L	>12.5 - 13.5 mg/dL; >3.1 - 3.4 mmol/L; Ionized calcium >1.6 - 1.8 mmol/L	>13.5 mg/dL; >3.4 mmol/L; Ionized calcium >1.8 mmol/L
Calcium Decreased (Hypocalcemia)	<LLN - 8.0 mg/dL; <LLN - 2.0 mmol/L; Ionized calcium <ULN - 1.0 mmol/L	<8.0 - 7.0 mg/dL; <2.0 - 1.75 mmol/L Ionized calcium <1.0 - 0.9 mmol/L	<7.0 - 6.0 mg/dL; <1.75 - 1.5 mmol/L; Ionized calcium <0.9-0.8 mmol/L	<6.0 mg/dL; <1.5 mmol/L; Ionized calcium <0.8 mmol/L
Albumin Decreased (hypoalbuminemia)	<LLN - 3 g/dL; <LLN - 30 g/L	<3 - 2 g/dL; <30 - 20 g/L	<2 g/dL; <20 g/L	
Alkaline Phosphatase increased	>ULN - 2.5 x ULN if baseline normal 2.0 - 2.50 x baseline if baseline abnormal	>2.5 - 5.0 x ULN if baseline normal >2.5 - 5.0 x baseline if baseline abnormal	>5.0 - 20.0 x ULN if baseline normal >5.0 - 20.0 x baseline if baseline abnormal	>20.0 x ULN if baseline normal 20.0 x baseline if baseline abnormal
Alanine amino transferase increased	>ULN - 3.0 x ULN if baseline normal 1.5 - 3.0 x baseline if baseline abnormal	> 3.0 - 5.0 ULN if baseline normal >3.0 - 5.0 x baseline if baseline abnormal	>5.0 - 20.0 x ULN if baseline normal >5.0 - 20.0 x baseline if baseline abnormal	>20.0 x ULN if baseline normal > 20.0 x baseline if baseline abnormal
Aspartate amino transferase increased	>ULN - 3.0 x ULN if baseline normal 1.5 - 3.0 x baseline if baseline abnormal	> 3.0 - 5.0 ULN if baseline normal >3.0 - 5.0 x baseline if baseline abnormal	>5.0 - 20.0 x ULN if baseline normal >5.0 - 20.0 x baseline if baseline abnormal	>20.0 x ULN if baseline normal > 20.0 x baseline if baseline abnormal

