Blood Bilirubin Increased	>ULN - 1.5 x ULN if baseline normal >1.0-1.50 x baseline if baseline abnormal	>1.5 - 3.0 x ULN if baseline normal >1.5-3.0 x baseline if baseline abnormal	>3.0 - 10.0 x ULN if baseline normal >3.0- 10.0 x baseline if baseline abnormal	>10.0 x ULN if baseline normal > 10.0 x baseline if baseline abnormal

Gamma Glutamyl Transferase Increased	>ULN - 2.5 x ULN if baseline normal 2.0 - 2.5 x baseline if baseline abnormal	>2.5 - 5.0 x ULN if baseline normal >2.5 - 5.0 x baseline if baseline abnormal	>5.0 - 20.0 x ULN if baseline normal >5.0 - 20.0 x baseline if baseline abnormal	>20.0 x ULN if baseline normal >20.0 x ULN if baseline abnormal
Creatinine Increased	>ULN – 1.5 x ULN	>1.5 - 3.0 x baseline; >1.5 – 3.0 x ULN	>3.0 baseline; >3.0 – 6.0 x ULN	>6.0 x ULN
Chronic Kidney Disease	eGFR (estimated Glomerular Filtration Rate) or CrCl (creatinine clearance) <LLN - 60 ml/min/1.73 m ² or proteinuria 2+ present; urine protein/creatinine >0.5	eGFR or CrCl 59 - 30 ml/min/1.73 m ²	eGFR or CrCl 29 - 15 ml/min/1.73 m ²	eGFR or CrCl <15 ml/min/1.73 m ²
Hypoalbuminemia	<LLN - 3 g/dL; <LLN - 30 g/L	<3 - 2 g/dL; <30 - 20 g/L	<2 g/dL; <20 g/L	
Proteinuria	1+ proteinuria	2+ and 3+ proteinuria	4+ proteinuria	

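### Three rows of the CTCAE grading limits in SAP Appendices 4 and 5 (haemoglobin in g/dL, low potassium Grades 1 and 2, GGT Grade 4) are wrong as written and need correcting before the Day 21 laboratory shift tables are programmed.

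*SAP*

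**What the plan says.** SAP 12.7.3 plans two sets of Day 21 shift tables against baseline, by treatment arm. One uses reference ranges (low, normal, high). The other is "based on CTCAE toxicity grade using version 5.0 or higher", with haematology limits taken from Appendix 4 and biochemistry limits from Appendix 5.

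- **Haemoglobin decreased (Appendix 4).** Each grade has three unit lines. The g/L lines run from LLN to 100, from 100 to 80, and below 80. The mmol/L lines run in parallel, with Grade 2 at "<6.2 – 4.9 mmol/L". The third line gives a Grade 1 limit of 10.0 g/L, a Grade 2 range of "<10.0 to 80.0 g/dL", and Grade 3 below 8.0 g/dL.
- **Potassium decreased (Appendix 5).** Grade 1 and Grade 2 both read "<LLN - 3.0 mmol/L". Grade 3 is "<3.0 - 2.5 mmol/L" and Grade 4 is below 2.5 mmol/L.
- **GGT increased (Appendix 5).** With an abnormal baseline, Grades 1 to 3 are multiples of baseline (2.0 to 2.5, above 2.5 to 5.0, above 5.0 to 20.0). The Grade 4 cell reads ">20.0 x ULN if baseline normal >20.0 x ULN if baseline abnormal".

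Section 12.7.3 converts laboratory values to standardized units but does not say which unit applies to haemoglobin.

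**The concern.** The two appendices are the grading specification that a programmer will code from. Haemoglobin, potassium and GGT are all scheduled tests (SAP Appendix 2; Protocol Table 9.2.12-1). If the limits contradict each other within a row, or two grades share one range, the grade a patient receives depends on an undocumented programming choice or is simply wrong. The tables compare nabiximols with placebo on safety. The SAP addendum, issued after early termination, appears to keep laboratory reporting as set out in the SAP, so the output is still due.

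**Working it through.** **Haemoglobin.** 1 g/dL = 10 g/L.

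- Grade 1 lower limit: the g/L line gives 100 g/L; the third line gives 10.0 g/L. Ratio 100 / 10.0 = 10 (too low).
- Grade 2 lower limit: the g/L line gives 80 g/L; the third line gives 80.0 g/dL = 80.0 × 10 = 800 g/L. Ratio 800 / 80 = 10 (too high).
- Grade 3: 8.0 g/dL × 10 = 80 g/L. This agrees with the g/L line.
- Check of the mmol/L line: 6.2 / 100 = 0.0620 and 4.9 / 80 = 0.0613. The mmol/L and g/L lines are consistent with each other.

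The next step applies each line literally to test values. The lower limit of normal is not in the documents; 120 g/L is assumed. The results for 90 and 75 g/L are the same for any LLN above 100 g/L.

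| Hb (g/L) | g/L line | Third line, literal | Third line, Grade 2 read as the range 10.0 to 80.0 g/dL |
|---|---|---|---|
| 140 | none | none | Grade 2 |
| 110 | Grade 1 | Grade 1 | Grades 1 and 2 |
| 90 | Grade 2 | Grade 1 | Grade 1 |
| 75 | Grade 3 | Grades 1 and 3 | Grades 1 and 3 |

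Read literally, Grade 2 on the third line is empty, since no value is both below 10.0 and at or above 80.0 g/dL. Read as a range, it captures a haemoglobin of 140 g/L, which is above the assumed LLN. With 10.0 g/dL (100 g/L) and 8.0 g/dL (80 g/L) put in, the third line agrees with the g/L line in all three grades.

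**Potassium.** Assumed LLN 3.5 mmol/L; the first result holds for any LLN above 3.2.

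- 3.2 mmol/L: Grade 1 and Grade 2.
- 2.8 mmol/L: Grade 3 only.
- 2.3 mmol/L: Grade 4 only.

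No criterion in the row separates Grade 1 from Grade 2, and no separating value can be derived from the documents.

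**GGT, abnormal baseline.** Illustration: baseline 10 × ULN, on-treatment 21 × ULN.

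- Against baseline: 21 / 10 = 2.1 × baseline, which is Grade 1 (2.0 to 2.5).
- Against ULN: 21 is above 20.0, which is Grade 4.

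If an abnormal baseline means one above ULN, then 20 × baseline always exceeds 20 × ULN. Any value above 20 × ULN that is between 2.0 and 20.0 × baseline therefore holds Grade 4 and a lower grade together. The ALP, ALT, AST and bilirubin rows set Grade 4 for an abnormal baseline as a multiple of baseline; GGT is the exception.

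**The case against.** The strongest reply is that little depends on these cells. Haemoglobin can be graded without ambiguity from the g/L or mmol/L lines, and the Grade 3 cell shows the intended cut. That stands, and it limits the haemoglobin error to the case where g/dL is the working unit. That case is open: the SAP names no unit for haemoglobin, and the neighbouring row for increased haemoglobin is given in g/dL only.

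For potassium, identical cells may reflect one cell spanning both grades, or a source criterion that was not carried over. The cited CTCAE text is not available here, so neither can be excluded. Either way, the SAP as it reads gives no rule for splitting the two grades. For GGT, the conflict needs a value above 20 × ULN in a patient with an abnormal baseline, and nothing in the documents suggests how often that will occur.

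Some characters in the text are lost in reading from PDF, so a single-letter slip such as g/L for g/dL in Grade 1 could be an artefact. That does not explain the Grade 2 figure of 80.0 g/dL. In the addendum table, the entry that keeps the SAP reporting is printed beside LLMT-4; that it covers laboratory data is the natural reading, but it is an inference.

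A reader might infer that the CTCAE shift tables as a whole cannot be graded. The documents do not support that. Potassium Grades 3 and 4 and most other rows are usable, and the reference-range shift tables do not draw on these appendices. A reader might also count the low ionized calcium entry, "Ionized calcium <ULN - 1.0 mmol/L", where ULN stands although total calcium in the same cell starts from LLN. It has no effect on the planned tables: the scheduled tests list only calcium, and 12.7.3 restricts summary tables to scheduled parameters and those derived from them.

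**Conclusion.** The point holds for three rows. The haemoglobin third line is out by a factor of 10 in two cells, so haemoglobin is misgraded if g/dL is the standardized unit. Low potassium from 3.0 mmol/L up to LLN falls in two grades at once. GGT Grade 4 with an abnormal baseline is on a different scale from Grades 1 to 3 and can overlap them.

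The impact is small. These are descriptive safety tables; no hypothesis test or efficacy endpoint uses the grades. Out-of-range values are also captured in the reference-range shift tables, the out-of-range summaries and the flagged listings. The number of patients affected cannot be derived from the documents. The assumed lower limits of normal serve only to illustrate; the contradictions within the rows do not depend on them.

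**What to change.** - **Haemoglobin:** in the third line, change the Grade 1 limit to 10.0 g/dL and the Grade 2 lower limit to 8.0 g/dL. Both follow from the row's own g/L values and meet the stated Grade 3 cut. Name the haemoglobin reporting unit in 12.7.3.
- **Potassium:** report values below LLN down to 3.0 mmol/L as one Grade 1-2 category, or reconcile the two cells with the cited CTCAE source. Leave Grades 3 and 4 as they are.
- **GGT:** express Grade 4 with an abnormal baseline as above 20.0 × baseline, in line with its own lower grades and with the other liver rows.
- **Ionized calcium:** change ULN to LLN in the low Grade 1 cell in the same pass, for tidiness only.

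The cost is a few table cells and one sentence on units, with no new data or analysis. Pooling potassium Grades 1 and 2 gives up a split that the present limits cannot make.
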